6 STATISTICAL METHODS

All data processing, summarization, and analyses will be performed using SAS® Version 9.4 or higher.

Unless otherwise specified, for continuous variables, descriptive statistics will include the number of participants/eyes (n), mean, standard deviation, median, minimum and maximum values. Categorical variables will be summarized using frequency and percentages.

Unless, otherwise stated, missing data will be handled as is, except when the aforementioned dates are required for calculations, the partial dates will have either '01' or 'Jan' imputed with an exception for dates related to AEs where the date closest to the last event (screening, first dose, last dose, etc.) should be used rather than arbitrary '01' of that month.

All efficacy data will be summarized by treatment group and time point using appropriate descriptive statistics. Summaries will be presented for both the mITT and PP populations. Due to the small number of participants that are expected to be enrolled at each center, all summaries and analyses will be performed using data pooled across centers.

Baseline results will be those recorded prior to dosing. In cases where more than one pre-dose observation has been recorded, the **last recording** will be identified as the baseline result.

Study days will be numbered relative to the date of the first dosing. The start of study (Day 1) will be defined as the date on which a participant takes the first dose of any study medication, as recorded on the CRF. Relative to study start, days will be numbered ...-2, -1, 1, 2, ... with Day - 1 being the day prior to the start of study medication (Pre-Dose).

Recorded data will be assigned to evaluation/assessment windows. If more than one clinical evaluation is made within a window for a particular visit, the record with the date closest to the targeted window will be used except for AEs where the **worst assessment** will be used.

Visit windows and analytical windows are defined as follow:

Visit	Targeted Window	Analytical Window
Pre-dose (Screening)	Day -14 to Day -1	Day -18 to Day -1
Visit 1 (First dosing date)	Day 1	Day 1
Visit 2 (optional)	Day 7 (± 3 day)	Day 2 to Day 16
Visit 3 (End of treatment visit)	Day 28 (± 3 days)	Day 17 to 3 days after the last dose and up to Day 42
Visit 4	Day 56 (± 5 days)	Day 43 to Day 70
Visit 5 (End of study visit)	Day 84 (± 5 days)	Day 71 to End of Study

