3.6 Concomitant Therapy

Ocular medications, other than artificial tears and ocular decongestants, are prohibited. Ocular decongestants must be washed out for a minimum of 7 days prior to baseline and use is prohibited 2 days before any study visit. Topical drops for examination procedures, such as anesthetics, dilating agents, fluorescein and lissamine green, are permitted.

Systemic medications that may interfere or confound the evaluation of conjunctival hyperemia are prohibited and should be washed out at least **7 days** prior to baseline. Washout should not commence until after written informed consent has been obtained. Refer to the Manual of Procedures (MOP) for examples of prohibited medications.

Medication considered necessary for the participant's welfare may be given at the discretion of the investigator and must be recorded in the eCRFs. Participants should be instructed to maintain a stable dose of chronic medications during the study whenever possible. All concurrent medications (prescription, over-the-counter and supplements), adjunct therapies, and concurrent procedures will be recorded on the appropriate eCRF page.

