4 STUDY PARAMETERS

4.1 Participant Disposition

Participants who completed the Day 84 visit will be considered as having reached Study Completion, otherwise, they will be classified in the Study Discontinuation group.

Reason(s) for discontinuation will be recorded and could include the following:

- Withdrawal of consent
- Administrative decision by the investigator or Sponsor
- Significant protocol deviation
- Participant noncompliance, or other significant protocol deviation

- Safety concern by the investigator or Sponsor
- Lost to follow-up

Time in the study will be computed as following:

Time in Study (Study duration) = Last Date in study – Date of First Dose + 1

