4.7 Safety Endpoints

The Medical Dictionary for Regulatory Activities nomenclature (MedDRA V21.0 at time of SAP publication, or the current version when superseded) will be used to code AEs.

Treatment-emergent AEs are any AEs with an onset date equal to or after the date of the first dose and **within 3 days** after the last dose of the study eye drop. A pre-existing event that worsens after the first dose date is considered a treatment emergent event. Treatment-related AEs are any AEs with a relationship of unlikely related, possibly related or related to study medication, or AEs with a missing relationship.

Safety endpoints include:

- Adverse events
- Concomitant medications
- Concurrent procedures
- Vital signs
- Laboratory tests (urinalysis, hematology, and serum chemistry parameters)
- Electrocardiogram
- Best-corrected visual acuity
- Intraocular pressure using a Goldmann applanation tonometer
- Biomicroscopy
- Tear film break-up time
- Lissamine green conjunctival staining
- Ophthalmoscopy

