6.2 Treatments

6.2.1 Extent of Study Drug Exposure

Exposure to treatment and treatment compliance will be summarized by the assigned treatment group.

Exposure (i.e., treatment time, days) will be determined as following:

$$\text{Time in Study Treatment (Treatment duration)} = \text{Date of Last Dose} - \text{Date of First Dose} + 1$$

Treatment compliance will be determined as study eye drops being used at least 70% of the time since last visit according to patient diary entries, AND at least 4 of the 6 scheduled applications in the 2 days prior to the visit.

Exploratory analyses will be conducted to understand the relationship between exposure and response.

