7.2 Study Days

Study days will be computed for each visit and AE event.

Study Days = Date of Visit/Event - Date of First Dose + 1

Or, if the visit/event occurs prior to the Day 1

Study Days = Date of Visit/Event - Date of First Dose

Date of First Dose is the Day 1 Visit date.

Last Date in study is the Day 84 Visit or the last visit where the participant was seen by the investigator. If lost-to-follow-up, the last date of contact is the Last Date in study.

If a participant had contact with the site after the final visit (e.g. for AE follow up), the last visit date will be the Last Date in study, not the contact date.

Time in Study (Study duration) = Last Date in study – Date of First Dose + 1

Time in Study Treatment (Treatment duration) = Date of Last Dose – Date of First Dose + 1

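### SAP 6 imputes a month-only date of last dose to the 1st of the month, which can give zero or negative exposure and a treatment-emergent window that closes before the first dose

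*SAP*

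**What the plan says.** SAP section 6 leaves missing data as they are, "except when the aforementioned dates are required for calculations"; in that case "the partial dates will have either '01' or 'Jan' imputed with an exception for dates related to AEs". For adverse events it substitutes another rule, "where the date closest to the last event (screening, first dose, last dose, etc.) should be used rather than arbitrary '01' of that month". Last dose appears in that exception only as an anchor for an adverse event date. Its own date is not exempted, and no other section gives a rule for it. SAP 6.2.2 has a partial-date rule for medications, but it only settles whether a medication is prior or concomitant.

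The date of last dose is then used in several places:

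- Exposure. SAP 6.2.1: "Exposure (i.e., treatment time, days) will be determined as following", with the formula repeated in SAP 7.2, where "Time in Study Treatment (Treatment duration) = Date of Last Dose" less the date of first dose, plus one.
- Treatment-emergent status. SAP 4.7: "Treatment-emergent AEs are any AEs with an onset date equal to or after the date of the first dose", with the window closing 3 days after the last dose. SAP 4.7.1 places later events in a separate post-treatment class.
- The upper limit of the Visit 3 analytical window in SAP 6.

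The date of first dose is the Day 1 visit date (SAP 7.2), so it should always be complete.

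**The concern.** For a start date, choosing the earliest possible day is a common convention. For an end date the same choice shortens the interval, and here nothing stops it from running past the beginning. The rule sets no floor at first dose, so it can return a last dose that precedes the first. That is an impossible value produced by a stated rule, not merely a detail left unspecified.

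SAP 6.6 rests the safety and tolerability conclusion partly on the incidence and severity of treatment-emergent events, and SAP 6.2.1 plans exposure-response analyses. An affected participant would enter the exposure summary with a zero or negative duration, and new events that arose on drug would leave the treatment-emergent tables. With groups this small, one reclassified participant moves a group's treatment-emergent rate by 1/20 = 5 percentage points at 20 per group, or about 4.3 points at 70/3 ≈ 23 per group.

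**Working it through.** **Inputs.** Exposure = last dose − first dose + 1 (SAP 6.2.1, 7.2). Treatment-emergent window = first dose to last dose + 3 days (SAP 4.7). Imputed day = 1 when only the month is known (SAP 6). Planned course = 28 days (protocol synopsis).

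**Check of the formula.** With complete dates, Day 28 − Day 1 + 1 = 28 days, which matches the planned course.

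**Condition for failure.** Let the first dose fall on day k of a month and the last dose later in the same month. The imputed last dose is day 1.

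- Exposure = 1 − k + 1 = 2 − k, which is zero or negative for k ≥ 2.
- Window end = 1 + 3 = day 4, which is before first dose for k ≥ 5.

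If the last dose falls in a later month, the window still ends after first dose, but too early.

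**Examples.**

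- First dose 10 June, true last dose 17 June, recorded as June: imputed 1 June. Exposure is 1 − 10 + 1 = −8 days instead of 17 − 10 + 1 = 8. The window ends on 4 June, six days before first dose.
- First dose 20 June, true last dose 10 July, recorded as July: imputed 1 July. Exposure is 12 days instead of 21. The window ends on 4 July instead of 13 July, so a new event from 5 to 13 July is displaced.

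**Frequency, given a month-only last dose.** Assume k is uniform on 1 to 30 in a 30-day month and the participant is on drug for d days. First and last dose share the month when k + d − 1 ≤ 30, that is k ≤ 31 − d.

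| d | Same month | Window empty (k from 5) | Exposure ≤ 0 (k from 2) |
|---|---|---|---|
| 5 | k ≤ 26 | 22/30 = 73% | 25/30 = 83% |
| 10 | k ≤ 21 | 17/30 = 57% | 20/30 = 67% |
| 20 | k ≤ 11 | 7/30 = 23% | 10/30 = 33% |

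**Second check on real calendar months.** Taking every 2019 start date with true durations of 1 to 27 days gives 365 × 27 = 9,855 combinations. The window ends before first dose in 44% and exposure is zero or negative in 54%. Exposure is understated by 14.7 days on average (range 0 to 30). By duration, the window ends before first dose in 67% (7 days), 44% (14 days), 21% (21 days) and 0% (28 days). If the month is missing too, the imputed date is 1 January and the window ends before first dose in about 95%.

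**With a corrected rule.** Setting the last dose to its latest possible day, capped only at the planned Day 28 and floored at first dose, leaves 0 of 9,855 windows ending before first dose. Exposure is then overstated by 9.6 days on average.

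**The case against.** The strongest reply is that a partial last-dose date should be rare. On Day 28 a dose is given in clinic (protocol 1.3 and 6.1.2), so completers have a dated dose. Others keep a daily diary (SAP 3.5), leave the study when they stop drug (protocol 7.1, SAP 6.2.3), and have exit procedures at the last visit they attend (protocol 7.2). Missing items are queried with the site (protocol 10.1.8), and queries are resolved before lock (protocol 9.4.1). A participant who disappears with the diary may have no last-dose date at all, which a partial-date rule does not reach. The reference to aforementioned dates also has no clear antecedent, so the rule's scope is uncertain. All of this stands and limits the reach of the point. It does not change what the rule does to a month-only last dose, which the calculations need and for which no other rule exists.

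The consequences are also softened. Displaced events go to the post-treatment tables by organ class, severity and relationship (SAP 4.7.1). Events leading to discontinuation have their own summary line, and listings show onset date and action taken (SAP 6.6.1). Efficacy data from a treatment-discontinuation exit are mapped to the next scheduled visit (SAP 6.2.3), so the primary endpoint is little affected despite the link to the Visit 3 window. SAP 4.7 would still count a pre-existing event that worsens after first dose.

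Three stronger readings are tempting, and the documents do not support them:

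- A reader might infer that time in study is corrupted too. SAP 7.2 defines the last date in study as a visit or, if lost to follow-up, the last contact. These are recorded by the site and normally complete.
- A reader might infer that month-only decongestant stop dates hide breaches of the 2-day restriction and keep participants in the per-protocol set. No section derives that restriction, or per-protocol membership, from imputed medication dates. SAP 5.4 uses major deviations and diary compliance, with exclusion rules settled before lock.
- A reader might infer that every error favours the active drug. The rule applies equally to vehicle, and treatment-emergent events lost from the vehicle group would make active drug look worse.

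**Conclusion.** The point holds as a defect in one stated rule applied to one date. A month-only last dose is set to a day that can precede the first dose, which makes exposure zero or negative and can empty the treatment-emergent window. The effect on safety reporting is misclassification from treatment-emergent to post-treatment; the events are not lost.

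The percentages are conditional: they apply only to participants whose last dose is known by month alone, and they assume first doses spread evenly over the month or year. The documents do not say how many such participants there will be; zero or a few are both compatible with the plan. The change is worth making before lock because the result is impossible as written and the repair is small. The point gives no reason to doubt the primary efficacy analysis.

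**What to change.** In SAP section 6, keep '01' and 'Jan' for partial start dates and add a separate sentence for the date of last dose. When it is partial, use the latest possible day of the known month or year, capped at the earlier of the Day 28 or exit visit and the last contact, and never earlier than the date of first dose. In the same edit, replace the reference to aforementioned dates with a list of the dates covered.

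The cost is a short text change and a small change to the derivation code. The downside is that exposure may be overstated for affected participants: by 9.6 days on average over true durations of 1 to 27 days when the only cap is the planned Day 28, and by less once the exit or last-contact cap applies. That error is conservative for capturing treatment-emergent events.

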### 9.2 SAMPLE SIZE DETERMINATION

As this is an exploratory study, an empirical sample size has been used.

Per sample size calculation using SAS Proc Power procedure, assuming the standard deviation of the mean overall hyperemia score is around 1.0, a study with 20 participants in each group (N=60)

should have at least 90% statistical power to detect a minimal difference of 1 in mean overall hyperemia scores among the three study groups at 95% confidence level.

For each of the 3 AG-86893 dose groups (vehicle, 0.1%, and 0.3%), approximately 20 participants with pterygium exhibiting conjunctival hyperemia are planned to complete the study. Therefore, a total of approximately 70 participants will be enrolled at up to 12 sites in order to achieve an estimated 60 evaluable participants after accounting for potential drop-outs. No more than a total of 70 participants will be enrolled in the study unless requested by Allgenensis.

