### 9.4 STATISTICAL ANALYSES

#### 9.4.1 GENERAL APPROACH

The database will be locked after all participants exit the study and all data clarification forms or queries have been resolved. Prior to database lock, a detailed Statistical Analysis Plan (SAP) will be finalized and approved. Final analysis and unmasking of participants' treatment code will occur after database lock.

Wherever appropriate, summary statistics will include the sample size, mean, standard deviation (SD), median, minimum, and maximum for continuous and ordinal variables, and frequency counts and percent for categorical variables. Data will be presented by treatment (0.1% AG-86893, 0.3% AG-86893, AG-86893 vehicle). Additional analyses between vehicle and active drug will be explored, the details of which will be described in the SAP. All testing will be two-sided and will be performed without adjustment for testing multiple measures.

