3.4 Randomization and Masking

Eligible participants will be assigned in 1:1:1 ratio into 1 of the 3 treatment groups. A central randomization scheme will be prepared by an unmasked Trial Runners representative and dispensed via an Interactive Web Response System (IWRS). Randomization schedule will be optimized as much as possible to achieve a balanced distribution of treatment assignment by investigational site, baseline hyperemia severity (grade of 2 vs. > 2), and PK participation.

Randomization assignment will occur by site personnel via IWRS once a participant's eligibility is determined by the investigator and confirmed by the central reading center. The IWRS will provide a unique Subject ID to be used in all study documents as the study identifier.

Study drug will be labeled with medication kit numbers, and the IWRS will provide each site with the specific medication kit number(s) for each randomized participant at the time of randomization. Sites will dispense study drug according to the IWRS instructions. Sites will receive the IWRS confirmation notifications for each transaction. All notifications are to be maintained with the study source documents.

Treatment assignment will be masked to the study participants, the investigators, all study-site personnel (with the exception of the unmasked drug administrator), study monitoring personnel, as well as Central Reading Center personnel during the entirety of the study. Day 28 efficacy and safety results based on the 1st database lock will be presented with unmasked treatment group, but no disclosure of treatment assignment at individual participant level.

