6.5 Efficacy Evaluation

All efficacy analyses will be based on the mITT population.

The primary statistical approach for assessment of difference among the treatment groups in change from baseline to Day 28 in conjunctival hyperemia score will be based on a mixed effect model. Significant baseline characteristics and their interaction might be included as covariant. Mean changes for each treatment group and the differences in mean changes will be estimated with the Least-Square means generated by the mixed model. Multiplicity adjustment will be conducted with Bonferroni approach.

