6.5.1 Primary Efficacy Variables

The primary endpoint is the change from baseline in overall conjunctival hyperemia score at Day 28, so, scores from Days 1 and 28 will be analyzed. The null hypothesis is that there is no difference between AG-86893 and AG-86893 vehicle in the change from baseline to Day 28 in the overall conjunctival hyperemia score. The alternative hypothesis is that the active group is different from vehicle in the change from baseline to Day 28 in the overall conjunctival hyperemia score. It was expected that the active group is at least 50% better than that of vehicle in the change of overall conjunctival hyperemia score.

To reserve the familywise error rate, the main treatment effect will be first assessed at the global level at $\alpha = 0.05$. If this is significant, then pairwise comparisons will be conducted using the Bonferroni adjustment for multiplicity between 1) 0.1% AG-86893 and AG-86893 vehicle; 2) 0.3% AG-86893 and AG-86893 vehicle; and 3) 0.1% AG-86893 and 0.3% AG-86893 for dose selection.

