APPENDIX 2 SAMPLE SAS CODE FRAGMENT

For estimation of main treatment effect:

SAS pseudo code for main treatment effect and LS mean estimation:

```
proc mixed data=xxx;  
  where mitt='Y'; *select the designated analysis population here (e.g.,  
  itt, pp);  
  class TREAT; *include other categorical covariants;  
  model CHANGE_OVERALL = TREAT/ddfm=statterth; *if any, include covariants  
  and interaction terms;  
  lsmeans TREAT/pdiff cl adjdfe=row adjust=bon;  
  (ods output statements)  
run;
```

SAS pseudo code for estimation of proportions and 95% CI, and the difference in proportions:

```
proc freq data=xxx;  
  tables VAR1 * VAR2/ alpha = 0.05 riskdiff (CL = MN);  
  * Miettinen and Nurminen inverted score test;  
  (ods statements)  
run;
```

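### The factors used to balance randomization are not pre-specified in the primary model, and the named mixed effect model has no random effect; if those factors are prognostic, the test is conservative and achievable power is forgone.

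*SAP*

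**What the plan says.** - **Allocation.** SAP 3.4 has the schedule optimized, as far as possible, for "balanced distribution of treatment assignment by investigational site, baseline hyperemia severity (grade of 2 vs. > 2), and PK participation". It names no blocking or minimization method.
- **Centers.** SAP 6 expects few participants per center and concludes that "all summaries and analyses will be performed using data pooled across centers". The rule is not confined to descriptive tables.
- **Model in the text.** SAP 6.5 says the primary comparison "will be based on a mixed effect model". It names no random effect. Baseline characteristics found significant, and their interactions, may be added.
- **Model in the code.** Appendix 2 gives "model CHANGE_OVERALL = TREAT/ddfm=statterth", with treatment the only named effect and no RANDOM or REPEATED statement. Comments in the code allow covariates, if there are any.
- **Protocol.** Section 9.3 specifies analysis of variance with dose as the main effect, which is what the code fits.
- **Gate.** SAP 6.5.1 tests globally at 0.05 and "then pairwise comparisons will be conducted using the Bonferroni adjustment for multiplicity between" the three pairs of arms.

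**The concern.** When arms are balanced within a factor, that factor's contribution largely cancels out of the treatment difference. A model that omits the factor still counts its variance in the residual. The reported standard error then exceeds the true one, confidence intervals are too wide, and the test rejects a true null less often than 5%. At 20 evaluable participants per arm the forgone precision matters most for the per-dose comparisons, which SAP 6.5.1 uses to select a dose.

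The text and the code also disagree. Without a random effect the model is not mixed, and the degrees-of-freedom options in Appendix 2 have nothing to act on. The only route by which a balancing factor could enter is a significance screen on the trial's own data, which is not pre-specification.

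**Working it through.** **Inputs from the documents.** 20 per group, SD 1.0 and a difference of 1 (Protocol 9.2); "All testing will be two-sided" (Protocol 9.4.1); global test at 0.05, then three pairs at 0.05/3 = 0.0167 (SAP 6.5.1); about 70 enrolled for 60 evaluable at up to 12 sites (Protocol 9.2, SAP 3.3). Protocol 9.2 states the SD for the score; it is applied here to the change.

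**Assumed input.** R² (for site alone, the ICC) is the share of outcome variance explained by the balanced factors. The documents give none; 0 to 0.30 is shown.

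**Step 1: the plan's own figure.** Protocol 9.2 says the trial "should have at least 90% statistical power to detect a minimal difference of 1 in mean overall hyperemia scores among the three study groups", taking alpha as 0.05. For group means (0, 0, 1) the noncentrality is 20 × (2/3) / 1² = 13.33. The F test on 2 and 57 df has power 0.8997. The 90% is therefore reproduced as an unadjusted three-group F test. A single Bonferroni pairwise comparison under the same inputs has power 0.754.

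**Step 2: closed form, balance fully achieved.** The treatment-only model reports SE = √(2/20) = 0.316. The true SE is 0.316 × √(1 − R²). The adjusted columns use residual SD √(1 − R²) and 57 − 13 = 44 df (11 for sites, 1 for severity, 1 for PK participation).

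| R² | True SE | Reported / true | Per-dose power, treatment only | Per-dose power, adjusted | Global power, adjusted |
|---|---|---|---|---|---|
| 0 | 0.316 | 1.00 | 75.4% | 74.7% | 89.5% |
| 0.10 | 0.300 | 1.05 | 76.8% | 79.7% | 92.5% |
| 0.20 | 0.283 | 1.12 | 78.2% | 84.7% | 95.1% |
| 0.30 | 0.265 | 1.20 | 79.7% | 89.6% | 97.3% |

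The per-dose gain is 2.9, 6.5 and 9.9 points at R² of 0.10, 0.20 and 0.30. At R² = 0 adjustment costs less than one point.

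**Step 3: simulation, good balance.** With 12 sites, blocks of three within site and 60 evaluable, the true size of the 5% global test without a site term is 4.4 / 2.8 / 1.9% at ICC 0.1 / 0.2 / 0.3. With both doses differing from vehicle by 1.0, a random site intercept moves global power from 90 to 93, 92 to 95 and 92 to 97%. Per-dose power moves from 76 to 80, 78 to 84 and 79 to 89%. At ICC 0 global power is 91% either way.

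**Step 4: simulation, imperfect balance.** SAP 3.4 promises balance only as far as possible. Three factors over 12 sites make 12 × 2 × 2 = 48 cells for about 70 participants. Three readings of this, each with 70 randomized and 60 evaluable, give the following true size without adjustment:

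| Scheme (assumed) | ICC 0.1 | ICC 0.2 | ICC 0.3 |
|---|---|---|---|
| Uneven sites (12 down to 1 participants), blocks of three within site, often incomplete | 4.3% | 3.6% | 2.3% |
| Blocks of three within all three factors (40% higher severity, 30% PK) | 4.7% | 3.9–4.0% | 3.2–3.4% |
| Uneven sites, blocks within site and severity | 3.9% | 3.4% | 3.0% |

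In the first scheme, fixed site effects restore the size to 5.0–5.2% and move per-dose power from 76 to 77, 78 to 82 and 78 to 87%. At ICC 0, however, fixed site effects cost about 4 points of power.

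**Step 5: severity.** In the third scheme, a severity term lifts global power from 90 to 94% at a severity R² of 0.2.

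**The case against.** - **Covariates are permitted.** SAP 6.5 allows them, and Appendix 2 is sample code whose comments leave room for them. A reader might infer that treatment must be the only term in the final model; the documents do not support that. What stands is narrower: the balancing factors are optional, would enter by significance, and for site the pooling rule points the other way.
- **The harm is conditional.** A reader might infer that the intervals are certainly too wide. That requires the factors to predict the change score. Central grading of photographs and a change-from-baseline endpoint may both keep the site share low. This stands, although the photographs are taken at the sites, and baseline severity is plausibly prognostic for a change score.
- **Balance may be loose.** This also stands. It roughly halves the size distortion at ICC 0.2 to 0.3 in one scheme, but the direction persists in all three.
- **Planned power is not lost.** Correct. The 90% was computed without adjustment and the treatment-only global test still delivers it. The loss is relative to a better model, in a trial described as exploratory.
- **Pooling has a stated reason.** Few participants per center is a good argument against fixed site effects, but a weaker one against a random intercept.
- **Omitting site inflates false positives.** A reader might infer this by analogy with cluster trials. Treatment is allocated to individuals, with balance sought within site, so the error runs the other way.

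**Conclusion.** The point holds as a pre-specification and efficiency defect. None of the three balancing factors is committed to the primary model, and the model named in SAP 6.5 is not the one coded in Appendix 2.

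For an assumed share of variance of 0.1 to 0.3 with imperfect balance, the 5% global test runs at roughly 3 to 4.5% (individual results 2.3 to 4.7%). Up to about 10 points of per-dose power are forgone, the top of that range needing a share of 0.3. At zero share there is no loss. There is no type I error inflation, and the planned 90% global power is not undermined. No gain has been shown for PK participation.

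Confidence is moderate: the textual gap is certain, but its size rests on an R² that the documents do not give and on a balancing method that they do not name.

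**What to change.** Amend the SAP before the first database lock, when SAP 8 schedules the primary analysis:

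- In SAP 6, limit the pooling rule to descriptive summaries.
- In SAP 6.5 and Appendix 2, add the severity stratum used at randomization as a fixed class effect and site as a random intercept (RANDOM intercept / subject=SITE). Fixed site effects are not advised with sites this small. If the site variance is estimated as zero, the intercept drops out.
- Replace the rule that admits covariates by significance with this fixed list, so that text and code describe one model.
- Treat the PK-participation flag as optional. PK sampling is done only at selected sites, so the flag overlaps with site.

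The cost is a few lines of SAP text and code, one or two degrees of freedom and slightly more modelling work. No new data and no change in conduct are needed.
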